Patients will be randomized in blocks of 6, stratified according to the etiologies: (idiopathic, diabetic, and post-surgical; patients after esophagectomy with gastric pull-through will not be included). Control visits will be scheduled at 3, 6, 12, 24, and 36 months. The primary outcome will be the proportion of patients with treatment success in the active group vs. sham group at 6 months after the procedure. Several secondary outcomes will also be assessed, including procedure-related parameters and safety parameters and change in Gastric Emptying Study (GET) after G-POEM vs. sham. After 6 months, patients randomized to the sham group will be offered G-POEM procedure and further followed up (cross-over part of the study) providing that they did not have a therapeutic effect of the sham procedure.

4. Introduction

Gastroparesis (GP) is relatively common gastrointestinal (GI) motility disorder, defined as epigastric symptoms associated with delayed gastric emptying (GE) in the absence of a mechanical obstruction. The prevalence of gastroparesis is unknown due to the difficulties inherent of undertaking true population-based studies. In a large study, the age-adjusted incidence of gastroparesis was 2.4 per 100,000 person-years for men and 9.8 per 100,000 person-years for women [2]. Women are more commonly affected than men [3]. In clinical practice, idiopathic and diabetic gastroparesis are the most common causes, each accounting for about one third of the patients [4]. While traditionally gastroparesis has been mainly associated with type 1 DM, the global rise of obesity-related diabetes has resulted in a high proportion of gastroparesis patients with type 2 DM. The cumulative incidence of developing gastroparesis in type 1 DM is 5.2% over 10 years and 1% in type 2 DM. Gastroparesis may also develop as a consequence of gastric or abdominal surgery or may accompany some other neurological, infectious, and infiltrative disorders [4-7]. Symptoms are not specific and may be mild, moderate or severe and include nausea, vomiting, dyspeptic symptoms, regurgitation, weight loss and poor nutritional status.

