6.3.2. Randomization

Patients fulfilling all inclusion criteria (and without exclusion criteria) will be asked to sign an informed consent form. Then, participants will be randomly allocated into the two groups:

- A. Group that will receive G-POEM (active arm), or
- B. Group that will receive sham procedure ("placebo" arm)

The patients will be stratified by the etiology of gastroparesis and gender. Patients will be randomised in blocks of 6. After signing an informed consent form, each centre will e-mail patient initials, birth date, patient's gender and etiology of gastroparesis (1= idiopathic or other, 2= diabetic; 3 = post-surgical) to a study nurse in Prague and she will send back as soon as possible the treatment allocation with patient's number. Patients will be randomized in 1:1 allocation ratio and patients must not be informed about their assignment.

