- 1. Proportion of patients with treatment success in the active arm at 3M, 12M, 24M and 36M.
- 2. Proportion of patients with treatment success in the sham group at 3M.
- **3.** Change in GSCI and PAGI-SYM before and after G-POEM at 3, 6, 12, 24 and 36M and before vs. after sham procedure at 3M and 6M; comparison of the change of the scores between the active and sham groups.
- **4.** Proportion of patients (randomized into the sham group and undergoing G-POEM after 6M) with treatment success after the sham procedure (6M) and after G-POEM (6M) cross over part
- **5.** Change in GSCI and PAGI-SYM before and after G-POEM vs. sham procedure in patients randomized to the sham group at 3 and 6M (cross over part)
- 6. Subgroup post-hoc analyses of the treatment success and change in symptomatic scores according to etiology of gastroparesis.
- 7. Change in gastric emptying (scintigraphy) study, EndoFLIP values and/or gastric emptying breath test before and after both G-POEM and sham procedure; comparison of the mean change of these parameters between active and sham groups.
- **8.** Procedure details (length of the procedure, technical success, perioperative adverse events).
- 9. Short- and long-term adverse events.

11. Sample size calculation

A total of 86 patients will be randomized.

- 43 patients will be randomized into the G-POEM group
- 43 patients will be randomized into sham group

Sample size calculation is based on expected therapeutic success of G-POEM in 50% of patients vs. 20% in the sham group; significance level 0,05; study power 0,8; beta error 0,2; adjustment for 15% expected drop out.

12. Statistical analysis

Data will be analyzed for both the intention to treat (ITT – a cohort for primary end point analysis) and the per-protocol population (sensitivity analysis). The per-protocol analysis will include only patients who will complete the entire follow-up. The efficacy of G-POEM at month 6 (main outcome) will be evaluated by Poisson regression with robust standard errors or similar regresion based approach. Baseline characteristics will be compared by using chi-squared tests for categorical variables and t-tests for continuous data.

The efficacy of treatment at other time points (3M, 12M, 24M and 36M) as well as the pooled efficacy cross-over + active groups will be evaluated similarly.

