Mean changes in the GCSI score and gastric emptying time in the active vs. control group will be analysed by ANCOVA. A p value less than .05 will be considered statistically significant. **An interim-analysis** will be performed when **40**% of patients will have completed the 6 months follow-up.

Statistical analysis plan

To prevent possible bias caused by the choice of statistical methods, this extended statistical analysis plan aims to adhere to the plan presented in the original version of the protocol while adding details of the planned analysis approaches.

The cohort for the primary analysis will be the intention to treat (ITT) population including all randomized patients according to their original allocation regardless of the actual treatment received or follow-up adherence to the protocol exhibited. Missing data in the ITT population will be imputed using the multiple imputation method. Further, the primary outcome will be analyzed on the per-protocol population to assess sensitivity.

The difference in efficacy of G-POEM versus sham at month 6 (main outcome) will be evaluated by logistic regression, same as the differences in treatment success at other time points (3M, 12M, 24M and 36M). Logistic regression will also be used to search for predictors of treatment success among other variables (age, sex, baseline values of scores, baseline GES, and EndoFLIP measurements).

Further, 95% confidence intervals for the point estimates of treatment success rates will be constructed using the Wilson method for G-POEM, sham, cross-over, pooled original + cross-over G-POEM groups and also etiology sub-groups at all time points.

Continuous secondary outcome variables will be presented as means or medians with 95% confidence intervals in dependence on the results of normality test for particular variables. The confidence intervals will be constructed using a bootstrapping method, which can be

conveniently combined with the multiple imputation approach even for estimation of the median, where normality is not assumed. Between group differences for the secondary outcomes will be tested using t-tests, possibly after data transformation for highly non-normal data.

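### The protocol names two models for its single confirmatory test, puts the randomisation factors in neither, and states the strata two ways

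*Protocol*

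**What the plan says.** Section 12, opening text: the efficacy of G-POEM at month 6 "will be evaluated by Poisson regression with robust standard errors or similar regresion based approach".

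Section 12, Statistical analysis plan sub-section: "The difference in efficacy of G-POEM versus sham at month 6 (main outcome) will be evaluated by logistic regression". Its introduction says that "this extended statistical analysis plan aims to adhere to the plan presented in the original version of the protocol while adding details". It does not say that it replaces the opening text. Covariates are listed only for an exploratory search for predictors of success. Sex is on that list and etiology is not. No covariate is named for the primary comparison. The same section makes 6-month success the one confirmatory hypothesis, at the 5% level.

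Section 3, Study Summary: "Patients will be randomized in blocks of 6, stratified according to the etiologies: (idiopathic, diabetic, and post-surgical".

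Section 6.3.2, Randomization: "The patients will be stratified by the etiology of gastroparesis and gender". The etiology codes there are "1= idiopathic or other, 2= diabetic; 3 = post-surgical", and the Summary has no category for other causes.

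The Study Summary also cites a prospective uncontrolled study in which success after G-POEM was 70-80% in idiopathic or post-surgical disease and 50% in diabetic disease.

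**The concern.** A confirmatory test should have one model, one effect measure and one covariate set, fixed in advance. Here the first text names a model that yields a risk ratio and then allows any similar regression. The second names a model that yields an odds ratio while claiming continuity with the first. Both are current.

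Randomisation is stratified because etiology is expected to matter, yet neither text carries the strata into the primary analysis. When strata are prognostic, an analysis that ignores them has standard errors that are too wide for the design, and it loses power. The factors to adjust for cannot be written down until Sections 3 and 6.3.2 agree on what they are.

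**Working it through.** **Inputs.** From Section 11: success 50% v 20%, significance level 0.05, power 0.8, 15% drop-out, 43 per arm. From Section 6.3.2: 1:1 allocation and blocks of 6. Sidedness is not stated; two-sided is assumed.

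**The plan's sample size.** The unpooled two-proportion formula gives n = (1.960 + 0.842)² × (0.50×0.50 + 0.20×0.80) / 0.30² = 7.849 × 0.41 / 0.09 = 35.76, so 36 per arm. Then 36 / 0.85 = 42.4, so 43 per arm and 86 in total. This matches the plan and does not depend on the point at issue.

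**Effect measure.** Risk ratio = 0.50/0.20 = 2.5. Odds ratio = (0.50/0.50)/(0.20/0.80) = 4.0.

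**The two tests on the same table.** Let a and c be successes and b and d failures in the two arms, with n per arm.
- Logistic Wald: log OR / √(1/a + 1/b + 1/c + 1/d)
- Robust Poisson Wald: log RR / √(1/a − 1/n + 1/c − 1/n)

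Exactly at the planned rates (21.5 v 8.6 of 43):
- logistic 1.386/0.488, p = 0.0045
- robust Poisson 0.916/0.341, p = 0.0072

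A borderline table, 20/43 v 11/43:
- logistic 0.928/0.464, p = 0.046
- robust Poisson 0.598/0.307, p = 0.052

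**How often they disagree.** Every possible table was enumerated and weighted by its binomial probability at 50% v 20%.

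| Per arm | Power, logistic | Power, robust Poisson | Opposite verdicts at 5% |
|---|---|---|---|
| 43 | 84.6% | 82.7% | 1.9% |
| 37 | 77.1% | 76.0% | 1.1% |
| 36 | 77.2% | 74.2% | 3.0% |
| 20 | not tabulated | not tabulated | 5.4% |

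The 20-per-arm row is close to the 41 patients randomised by the interim review. The change between 36 and 37 shows that part of the gap comes from the discreteness of the tables.

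**Direction.** At the planned rates, every disagreement that carries any real probability has logistic significant and robust Poisson not. The reverse occurs only when success exceeds 80% in both arms. An example is 41/43 v 35/43, where the same formulas give p = 0.061 (logistic) and 0.049 (robust Poisson). Taking the more favourable of the two is therefore, in practice, the same as always using logistic.

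**Type I error of the logistic Wald test.** At 43 per arm it is 4.3% when both arms have 20% success and 5.0% when both have 35%. At 20 per arm it is 2.3% to 4.1%. The likelihood-ratio test from the same logistic model, which the plan neither names nor excludes, gives 5.3% and 5.4% at 43 per arm.

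**Strata.** Three etiologies give 3 strata, on average 86/3 ≈ 29 patients each. Adding gender gives 6, on average 86/6 ≈ 14.

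**Omitting the strata.** This was simulated with blocks of 6 within three etiology strata, an assumed 40/30/30 mix, and an assumed log-odds gap of 0, 1 or 2 between the outer strata (about 1,500 runs each).

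| Gap | Power, unadjusted | Power, adjusted | Type I, unadjusted | Type I, adjusted |
|---|---|---|---|---|
| 0 | 87% | 87% | 6.0% | 6.5% |
| 1 | 84% | 85% | 4.1% | 4.5% |
| 2 | 77% | 82% | 3.8% | 5.5% |

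Monte Carlo error on the type I figures is about 0.6 points. The exact enumeration puts the unadjusted test at or below 5%, so the 6.0% at zero gap reads as simulation noise. The unadjusted test grows more conservative as the gap widens.

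For scale, the cited 70-80% v 50% is a log-odds gap of log(0.7/0.3) = 0.85 to log(0.8/0.2) = 1.39, nearest the middle row.

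**The case against.** The strongest reply on the model is that the text largely settles it. The open-ended alternative in Section 12 arguably covers logistic regression, and the later, more specific sub-section names logistic and nothing else. The interim analysis had to use the same tools as the final one, and the data and safety monitoring report does give a logistic p-value. This stands as far as it goes: logistic is the evident intention. It does not remove the first text, and it does not fix an effect measure.

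On adjustment, silence is not a statement that the analysis is unadjusted, and covariates are often left to a separate plan. That also has force. But this protocol contains its own extended plan, which names covariates for the predictor search and stops there. Baseline GCSI is a different matter: it is not a stratum, and it already enters the endpoint through percentage change, so adjusting for it is optional.

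Three stronger readings are tempting and are not supported:
- **That two models allow a false-positive result to be picked after the fact.** For the two named unadjusted Wald tests, the enumeration shows type I error staying at or below 5% at the null rates checked.
- **That the other model would have changed the interim recommendation.** The report gives p = 0.003 from logistic regression but no counts by arm, so the robust Poisson p-value cannot be computed.
- **That adjustment is worth a stated share of extra patients.** That needs the share of outcome variance explained, which the protocol does not give. The cited etiology difference comes from one uncontrolled study and says nothing about response to sham.

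**Conclusion.** The point holds at moderate severity. The protocol gives two unreconciled models for its only confirmatory test and two versions of the strata, and it does not put the randomisation factors in the primary model.

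The model choice is worth about 2 points of power at 43 per arm and determines whether the headline is a risk ratio or an odds ratio. The planned Wilson intervals for the success rate in each arm soften the second effect, because absolute rates will be seen either way. Omitting the strata costs about 0, 1 or 5 points of power across the assumed etiology gaps, and it errs on the conservative side.

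The model comparison rests on the planned 50% v 20%, two-sided 5%, Wald tests, complete data and equal arms. The strata figures rest on an assumed etiology mix and assumed gaps.

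**What to change.** 1. In Section 12, delete the robust Poisson sentence and its open-ended alternative.
2. State one primary model: logistic regression of 6-month success on arm and the stratification factors actually used. Baseline GCSI may be added but need not be. Specify a penalised fit if cells are sparse, and say which test of the arm effect gives the confirmatory p-value.
3. Name one effect measure, a marginal (standardised) risk difference or risk ratio, with its 95% confidence interval. Compute it within each imputed data set and then combine, since the plan uses multiple imputation.
4. Check the randomisation list, then make Section 3 and Section 6.3.2 state the same factors and the same etiology categories, including where other causes belong.

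The cost is wording only, with no change to the 86 patients. The one downside is a few more parameters. With etiology and gender, the model has five (intercept, arm, two for etiology, one for gender) against about 43×0.50 + 43×0.20 ≈ 30 expected successes, which is why the penalised fallback should be written in.

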15.1. Ethical considerations

The study will be conducted according to the Declaration of Helsinki, adopted by the 18th WMA General Assembly, Helsinki, Finland, June 1964, and amended by the 59th WMA General Assembly, Seoul, October 2008. Approval of the medical ethical committee or Institutional Review Board of all participating centers will be obtained. The DSMB in Prague (see above) will function as independent safety monitoring board and will receive written study reports of study outcomes and follow-up. All patients are required to sign a written informed consent form prior to randomization. Study patients can leave the study at any time for any reason without consequences. The study protocol, patient information and informed consent form and all other necessary documents (study amendments) will be submitted together with an appropriate request form to Ethical Committees (or IRB) for approval at each participating centre.

15.2. Patient Information and Informed Consent

Each patient will be informed adequately about content, consequences and risks of the study. This will happen by a standardized consent form, as well as verbally by a study investigator at each centre. It is the responsibility of the principal investigator or his assigned co-investigators to obtain signed informed consent according to the international standards

(including data management and security) from each patient before inclusion into the study. Patients will be given the opportunity to ask any questions that might arise. The informed consent form will be filled single-handed by the patient. The original remains at the study site, the patient will be handed a copy.

15.3. Data security

Only anonymous data will appear in any publication. Regulations of data security of the countries of the participating centres will be adhered to. Patients will be informed that their data will be pseudonymized according to documentation obligations and notification duties by §§ 12 and 13 GCP enactment. Patients who will not agree with these regulations will not be enrolled. Patients will be provided with a code during the randomization process. For data management, only pseudonymized data will be provided to the main study centre (Prague).

15.4. Administrative Aspects and Adverse Events recording

Patients will be coded using a numeric randomization code (anonymized) and only anonymized data will be submitted to the PI site (Prague) for data management. Adverse events (AE) and serious adverse events (SAE) (**Appendix 8**) will be reported to the coordinating study centre and there to the DSMB and the study steering committee (see below) to control safety issues and to discuss intervention or protocol amendments accordingly. An adverse event is any undesirable event that occurs whether or not considered to the participation in the study. Therefore, AEs can be any undesirable, unintentional, or unanticipated outcome or symptom or any disease in a timely relation to the study participation, independent of a suspected relation.

AE will be documented on designated CRF forms. A serious adverse event is defined as any event within the study timeframe fulfilling at least one of the following criteria:

- Death
- Live-threatening event
- Hospitalisation (required or prolonged)
- Event that results in disability
- Any event that an intervention to prevent one of the points above...

According to ICH-GCP guidelines, SAE(s) have to be reported within 24hours by email ([contact], copy: [contact]). SAE have to be reported to the local ethics committee of the study site.

CRFs as well as all study related documents will be kept at least 10 years after study termination. Any study subject is allowed to withdraw her / his consent for study participation at any time for any given reason.

16. References

- 1. Revicki, D.A., et al., Gastroparesis Cardinal Symptom Index (GCSI): development and validation of a patient reported assessment of severity of gastroparesis symptoms. Qual Life Res, 2004. 13(4): p. 833-44.
- 2. Jung, H.K., et al., *The incidence, prevalence, and outcomes of patients with gastroparesis in Olmsted County, Minnesota, from 1996 to 2006.* Gastroenterology, 2009. 136(4): p. 1225-33.
- 3. Dickman, R., et al., Gender aspects suggestive of gastroparesis in patients with diabetes mellitus: a cross-sectional survey. BMC Gastroenterol, 2014. 14: p. 34.
- 4. Langworthy, J., H.P. Parkman, and R. Schey, *Emerging strategies for the treatment of gastroparesis*. Expert Rev Gastroenterol Hepatol, 2016. 10(7): p. 817-25.
- 5. Davis, B.R., et al., *The Long-Term Efficacy and Safety of Pyloroplasty Combined with Gastric Electrical Stimulation Therapy in Gastroparesis.* J Gastrointest Surg, 2016.

Appendix 2. Questionnaires

GSCI score

		none	Very mild	Mild	Moderate	Severe	Very severe
1.	Nausea	0	1	2	3	4	5
2.	Retching	0	1	2	3	4	5
3.	Vomiting	0	1	2	3	4	5
4.	Stomach fullness	0	1	2	3	4	5
5.	Not able to finish a normal sized meal	0	1	2	3	4	5
6.	Feeling extensively full after meals	0	1	2	3	4	5
7.	Loss of appetite	0	1	2	3	4	5
8.	Bloating	0	1	2	3	4	5
9.	Stomach or belly visibly larger	0	1	2	3	4	5

- 1-3 = nausea/vomiting
- 4-7 = post-prandial fullness/early satiety
- 8-9 = bloating

Calculation:

Total GSCI score = arithmetic mean of the three symptom subscales Subscores = arithmetic means of (1-3), (4-7) and (8-9)

PAGI-SYM score

	None	Very mild	Mild	Moderate	Severe	Very
	_		_	_	_	severe
Heartburn (burning pain rising in your chest or throat) during the day	0	1	2	3	4	5
2. Regurgitation or reflux (fluid or liquid from your stomach coming up into your throat) during the day	0	1	2	3	4	5
3. Heartburn (burning pain rising in your chest or throat) when lying down	0	1	2	3	4	5
4. Regurgitation or reflux (fluid or liquid from your stomach coming up into your throat) when lying down	0	1	2	3	4	5
5. Feeling of discomfort inside your chest during the day	0	1	2	3	4	5
6. Bitter, acid or sour taste in your mouth	0	1	2	3	4	5
7. Feeling of discomfort inside your chest at night (during sleep time)	0	1	2	3	4	5
8. Vomiting	0	1	2	3	4	5
9. Nausea (feeling sick to your stomach as if you were going to vomit or throw up)	0	1	2	3	4	5
10. Retching (heaving as if to vomit, but nothing comes up)	0	1	2	3	4	5
11. Stomach fullness	0	1	2	3	4	5
12. Not able to finish a normal-sized meal	0	1	2	3	4	5
13. Feeling excessively full after meals	0	1	2	3	4	5
14. Loss of appetite	0	1	2	3	4	5
15. Bloating (feeling like you need to loosen your clothes)	0	1	2	3	4	5
16. Stomach or belly visibly larger	0	1	2	3	4	5
17. Upper abdominal (above the navel) discomfort	0	1	2	3	4	5
18. Upper abdominal (above the navel) pain	0	1	2	3	4	5
19. Lower abdominal (below the navel) pain	0	1	2	3	4	5
20. Lower abdominal (below navel) discomfort	0	1	2	3	4	5

- 1 7 = heartburn/regurgitation
- 8 10 = nausea/vomiting
- 11 14 = post-prandial fullness/early satiety
- 15 16 = bloating
- 17 18 = upper abdominal pain
- 19 20 = lower abdominal pain

Calculation:

Subscale scores are calculated by averaging across items comprising the subscale; scores vary from 0 (none or absent) to 5 (very severe). The half-scale rule is applied for missing data (i.e., the subscale score is calculated by using the mean of non-missing items; when more than 50% of items are missing, the score is set to missing).

A total score is calculated by averaging all subscale scores.

